## **RISKS AND DISCOMFORTS**

### **The SmartPill Capsule:**

Risks of the ingestion and passage of the capsule through the GI tract are minimal. Currently, several other diagnostic capsules, the Given PillCam and the Heidelberg pH capsule, are FDA released medical devices. The SmartPill is similar in size and shape to the Given capsule and, therefore, poses similar risk. In the 435 healthy and 443 non-healthy individuals who have ingested the Heidelberg pH Capsule, there were no complications in the healthy subjects and one complication in the non-healthy subject. This complication involved a patient with pyloric stenosis, and the capsule was retrieved through endoscopy

An estimated 170,000 capsule endoscopies have been performed since Given Imaging introduced the first ingestible endoscopy capsule for human use in 2000. Today, capsule endoscopy is considered a generally well tolerated and safe procedure. The primary hazard of the procedure is capsule retention. Retention incidence, as determined by a review of published studies of capsule endoscopy in adults, is estimated as 0.75% in patients without known stenosis and 21% in patients with known stenosis. Stenosis and strictures can be complications in inflammatory bowel disease (IBD).

Adverse events and functional technical issues with the SmartPill device may occur during the conduct of the study. The capsule may fail to empty from the stomach and fail to be expelled from the GI tract. Subjects ingesting the capsule or the meal may have nausea, vomiting, aspiration of the capsule or meal, abdominal pain, diarrhea or constipation. In previous studies with adult subjects (n=326), a total of 28 adverse events were reported: 19 were not device related, 7 were probably not device related, 1 was possibly related (sub-sternal pain) and one was definitely related. The one definitely related adverse device effect occurred when the capsule

failed to empty the stomach after 9 days due to entrapment in a bulk forming agent ingested by the subject. The capsule subsequently emptied the stomach after treatment with Erythromycin and passed naturally within 24 hours.

In this study, the exit of the capsule from the GI tract will be confirmed for each subject by examination of the data from the SmartPill study. If the capsule has not passed 5 days after ingestion and confirmation of exit cannot be determined by the SmartPill data, a qualified gastroenterologist will clinically evaluate the study subject and intervene if necessary. Interventions could include use of a laxative to promote capsule transit through the GI tract, endoscopy to retrieve the capsule if within reach of an upper endoscope or colonoscope, or surgical consultation if the capsule appears to be lodged within the small intestine.

Clinical adverse events such as difficulty in device ingestion, vomiting, gastric sensations, and gastric distress shall be assessed during the ingestion day visit. The capsule may fail to empty from the stomach after 8 to 24 hours. The capsule may also fail to pass from the GI tract after 7 days. Subjects ingesting the capsule or the meal may have nausea, vomiting, aspiration of capsule or meal, abdominal pain, diarrhea or constipation.

#### **Risks of the Washout Period**

Prior to the SmartPill initiation, patients will discontinue many of their gastrointestinal medications. During this washout period, the patient's bowel symptoms may get worse.

#### **Risks of Endoscopic Mucosal Resection**

Patients enrolled in the study will have one additional low risk procedure (EMR) at the time of their sigmoidoscopy. Patients who warrant a sigmoidoscopy will be asked to participate. Sedation should improve the discomfort of the EMR, but has a risk of complications (primarily low BP, slowed heart rate or respirations) of approximately 1/100. EMR is a common procedure in gastroenterology with a low risk for rectal lesions. In this procedure, one additional small piece of rectal tissue will be obtained for diagnosis.

The risk of one small EMR in the rectum has not been studied in large groups of patients. The risks of EMR in patients with large polyps in the rectum or with large superficial rectal neoplasms vary in the literature. Many smaller studies report no perforations or hemorrhages as a result of EMR. In one large study of EMR for colorectal neoplasia and polyps in 1000 patients, the rate of perforation was 0.2% and bleeding was 2%. **Error! Bookmark not defined.** Large Japanese series with colorectal tumors have reported a perforation rate 0.35% (3/863) and a bleeding risk of 1.16% (10/863) with colonic EMR. **Error! Bookmark not defined.** The risk of one small EMR in the rectum has not been studied in large groups of patients, but presumably has a lower risk than that seen with large resections or piecemeal removal of colonic tumors. There is no psychosocial risk associated with the intervention (EMR). Infants, children age 17 or less, and pregnant or nursing women will not be participating in the trial.

After the procedure, the analysis involves only the pathologic specimens. There is no long-term follow-up of patients for the purposes of this protocol. All enrolled patients will have the same procedure. The intervention in this trial is a one-time event. If a patient does not tolerate sigmoidoscopy or sedation, the procedure may be aborted at the discretion of the endoscopist and

anesthesiologist, in which case the EMR would not be performed. The patients will all receive best standard of care treatment at all times during the study. A patient will be removed from participation in the trial at any time if they request withdrawal.

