### **Follow Up Visit (Visit 3)**

This study visit should take about 30-45 minutes to complete and will take place 5 to 7 days after Visit 2.

At this visit, the patient will return the SmartPill receiver and the study diary. We will discuss any questions or concerns they had about the study. If available, we will review the results of the SmartPill test. If it is unclear that the capsule has passed, based on the subject's history or on the study results, we may prescribe erythromycin as a promotility medication or obtain a KUB for verification.

If the patient cannot return the receiver in person, they will be provided with information on mailing the receiver back. Once the results have been reviewed, the patient will be contacted to provide the results of the SmartPill and confirmation of capsule exit.

If the patient is appropriate for the endoscopic mucosal resection, this will be scheduled within the following 3 weeks.

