### **Sigmoidoscopy and Endoscopic Mucosal Resection (Visit 4)**

This study visit should take about 3.5 hours to complete.

This study visit consists of a sigmoidoscopy with biopsies and an endoscopic mucosal resection. When additional workup of gastrointestinal symptoms is warranted for altered bowel habits and/or abdominal pain, a subset of 15 treatment naive patients or with less than 6 months of treatment will be recruited from those who completed the SmartPill study for a sigmoidoscopy with biopsy collection and additional endoscopic mucosal resection.

The patient will fast the night prior and receive 2 enemas the morning of the procedure. The patient will present for completion of a clinically needed sigmoidoscopy with routine rectal and sigmoid biopsy collection. In addition, an endoscopic mucosal resection will be completed in the rectum. Biopsies will be sent to pathology for the following analysis.

1. Light microscopy with hematoxylin and eosin, periodic acid schiff, toluidine blue and acetylcholine staining.
2. Electron microscopy
3. Immunohistochemistry staining with anti-Gb3 monoclonal antibody.

All specimens will be examined for cellular morphology, other significant noted injury or structural abnormalities and location of deposition. The biopsies will be specifically analyzed for vascular and neuropathic changes. The specimens will be assessed for presence or absence of neuronal swelling, myelination, vascular sclerosis, intimal fibrosis and hypertrophy of the smooth muscles of the arterioles. The neurological and vascular cells will be assessed for deposition and quantification will be determined based on a degree of deposition scale used previously for renal biopsy analysis in Fabry disease (0 No deposit, +deposit present in a few cells, ++ deposits present in some cells, +++ deposits present in many cells) (Valbuena et al., 2008). Finally, results of analysis of all specimens will be compared to healthy aged-matched controls obtained from banked specimens in the pathology department. Once the analysis is completed, results will be correlated with the patient's gastrointestinal symptom presentation.

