### **Patients Travelling from Out of State**

Prior to scheduling the visit, the patient will be provided with an electronic copy of the consent form in accordance with Partners Information Security guidelines. They will be advised to read it over. The study staff will then contact the patient after a couple days and answer any questions the patient may have about the study and can be put in contact with the physician. The patient will be notified of all medications that needs to be stopped for the SmartPill and if eligible, for the sigmoidoscopy. All information for the sigmoidoscopy will be sent to the patient and the subject can be put in contact with a physician to answer any additional questions. If the patient agrees, the condensed visit will be scheduled.

The scheduled visit will be a condensed visit consisting of visit 1 and visit 2. The patient will be provided with information regarding mailing the receiver back to the study staff.

If the patient is eligible for the EMR, the visit will be condensed into 2 days. On the first day, the scheduled visit will include the screening visit (visit 1) and the sigmoidoscopy and EMR (visit 4). The patient will be consented by the physician prior to conducting the medical history and physical and completing the questionnaires. After, the patient will be prepped for the sigmoidoscopy and EMR. On the second day, the SmartPill visit will be conducted. This option will also be available for patients who are in state but cannot travel to the hospital multiple times.

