### **SmartPill Study Procedure**

Patients taking gastric acid suppressants will be instructed to stop proton pump inhibitors 1 week prior to the colonic transit study and histamine type 2 receptor antagonists 3 days prior to the colonic transit study. Patients with constipation will stop treatments for constipation at least 72 hours prior to the study and for the 5 days of the study. This includes enemas, cathartics, PEG solutions (including Miralax, enulose). Patients with constipation may take medications to help stimulate a bowel movement with either milk of magnesia, 2.4 to 4.8 grams (30-60 ml), or magnesium citrate, 11 to 25 grams daily in 1 or more doses, up to 48 hours prior to SmartPill ingestion.

All study subjects will report for the ingestion visit after an overnight fast (beginning at midnight). Date of the start of the last menstrual period for female subjects will be recorded.

The SmartPill capsule will be activated and calibrated. All study subjects will ingest a SmartBar (a nutritional bar) consisting of approximately 254 calories with 120 cc of water, followed by the SmartPill Capsule with 50 ml of water. The subject may drink an additional 50 ml of water if difficulty swallowing capsule for a total of 100 ml with capsule ingestion. Ingestion of the meal, SmartPill Capsule, and water should be completed within 10 minutes.

Intraluminal GI tract pH, pressure, temperature will be measured continuously with the SmartPill capsule. Once the capsule is ingested the patient is free to leave to the facility. At 8 hours after capsule ingestion, with the subject in a sitting position, one can of regular Ensure (Vanilla, lactose-free, 8 fluid ounces [237 ml]; 250 calories) will be ingested.

All study subjects will maintain a diary and will record times of bowel movements, meals, gastrointestinal symptoms (pain/discomfort, nausea, vomiting), and supine/sleeping times. Subjects will be instructed, if they wish, to recover and return the SmartPill capsule along with the diary and receiver at the end of the study. If they are unable to return to the office due to distance, they will be given material to send the items via FedEx.

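### In the standard visit sequence, no study contact is described after the research-added rectal resection, so no planned check would pick up a delayed bleed or perforation

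*Combined protocol and SAP*

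**What the plan says.** **Standard sequence.** Study Procedures plans three visits and a possible fourth. At Visit 3 the capsule receiver and diary come back, and then: "If the patient is appropriate for the endoscopic mucosal resection, this will be scheduled within the following 3 weeks". Visit 4 is the sigmoidoscopy with routine biopsies, and "In addition, an endoscopic mucosal resection will be completed in the rectum". The Visit 4 section goes on to the pathology work and describes no later visit or call. Risks of Endoscopic Mucosal Resection adds: "After the procedure, the analysis involves only the pathologic specimens. There is no long-term follow-up of patients for the purposes of this protocol".

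**Two-day schedule.** This is for out-of-state patients and for local patients who cannot make repeated trips (Patients Travelling from Out of State). Screening and EMR are on day one, and "On the second day, the SmartPill visit will be conducted". The receiver is then returned or mailed. For those who mail it, "Once the results have been reviewed, the patient will be contacted to provide the results of the SmartPill and confirmation of capsule exit".

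**Safety provisions.** Risks of Sedation has vital signs monitored during the procedure. The monitoring and quality assurance section has adverse events reported at once and outcomes reviewed as the study proceeds. The EMR risk section promises standard-of-care treatment throughout. On the capsule side, "Clinical adverse events such as difficulty in device ingestion, vomiting, gastric sensations, and gastric distress shall be assessed during the ingestion day visit".

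**The concern.** The EMR is the most invasive step the study adds. The protocol calls it low risk, but it also acknowledges that a single small rectal EMR lacks large-group data, and it presumes rather than shows that the risk is below that of the tumour and polyp series it cites. A bleed or perforation may declare itself after the patient has gone home. An instruction to report events at once works only if someone learns of them, and the visit schedule gives the study no occasion to ask.

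The capsule is handled differently. The protocol describes its risks as minimal, yet exit is confirmed for every subject, and a gastroenterologist evaluates anyone whose capsule has not passed by five days when the data cannot settle the matter. The resection has no counterpart.

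Two things are at stake: prompt attention for an individual patient with a complication, and a complete event record for the procedure.

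**Working it through.** **1. Contacts after EMR, by schedule.**

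| Schedule | Described contacts after EMR | Stated content |
|---|---|---|
| Standard (Visits 1, 2, 3, then 4) | None | Not applicable |
| Two-day (Visits 1 and 4, then 2) | SmartPill visit next day | Adverse-event assessment; examples concern swallowing, vomiting and gastric symptoms |
| Two-day | Diary during recording | "All study subjects will maintain a diary and will record times of bowel movements, meals, gastrointestinal symptoms (pain/discomfort, nausea, vomiting), and supine/sleeping times" |
| Two-day | Visit 3, or mailed receiver and results contact | Questions or concerns; capsule results and exit |

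On the two-day schedule, contacts exist but none is described as an EMR check, and the diary does not list bleeding. Pain is also ambiguous, because the capsule section warns: "Subjects ingesting the capsule or the meal may have nausea, vomiting, aspiration of capsule or meal, abdominal pain, diarrhea or constipation". No planned question separates the two sources.

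**2. Inputs for the size of the risk.** n = 15, the maximum in Recruitment Procedures. The complication rates come from Risks of Endoscopic Mucosal Resection:

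- 1000-patient series: bleeding 2%, perforation 0.2%.
- 863-case series: bleeding 10/863 = 1.16%, perforation 3/863 = 0.35%. Both printed percentages reproduce.

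**3. Expected events, n × rate.**

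- Bleeds: 15 × 0.0116 = 0.17; 15 × 0.02 = 0.30.
- Perforations: 15 × 0.002 = 0.03; 15 × 0.0035 = 0.05.

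**4. Chance of at least one event of one kind, 1 − (1 − rate)^15.**

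- Bleeding: 16.0% at 10/863; 26.1% at 2%.
- Perforation: 3.0% at 0.2%; 5.1% at 3/863.

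**5. Chance of at least one event of either kind, 1 − [(1 − b)(1 − q)]^15**, where b is the bleeding rate and q the perforation rate. This takes patients as independent and the two complications as independent within a patient.

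| b | q | Source | Result |
|---|---|---|---|
| 1.16% | 0.2% | Lowest of each | 18.5% |
| 1.16% | 0.35% | 863-case series | 20.4% |
| 2% | 0.2% | 1000-patient series | 28.3% |
| 2% | 0.35% | Highest of each | 29.9% |

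These are chances that an event occurs, not that it is missed.

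**6. What 15 patients can show.** With no events in 15, the one-sided 95% upper limit on the event rate is 1 − 0.05^(1/15) = 18.1%. Asking patients afterwards protects them and completes the record. It would not establish that the procedure is safe.

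**The case against.** The case against has several parts.

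- **The sentence about follow-up excludes only the long-term kind.** This is correct. A reader might infer that the protocol rules out all contact after EMR, but it does not. The gap is an inference from the visit schedule, which is laid out in full and ends at Visit 4.
- **Instructions or an emergency number may sit elsewhere.** The consent and contact pages, and the Protocol Summary mentioned under Recruitment Procedures, were not available for this review. If a post-procedure call is specified there, a cross-reference is enough.
- **These patients remain under care.** A reader might infer that they are not seen again after Visit 4. The documents do not support that: patients come from the hospital's own Fabry clinic or through treating physicians, the sigmoidoscopy is clinically needed, EMR is in frequent use at the hospital, and standard-of-care treatment is promised. Routine care may well find a serious complication. It remains true that nothing has the study ask about events or record the answers.
- **The two-day schedule is largely covered.** Much of this stands. Adverse events must be assessed the day after EMR, and the listed examples are open-ended, so bleeding is not excluded. What is missing is a specific question.
- **The risk is low.** The protocol cites many smaller studies with no perforation or hemorrhage and presumes a lower risk than in the large series. The figures above are therefore probably at the upper end.

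**Conclusion.** The point holds as a minor patient-safety improvement. As the schedule is written, a patient on the standard sequence has no study check for delayed bleeding or perforation after a resection added for research. Detection depends on the patient or on routine care. At the cited rates the chance of at least one such event among 15 patients is 18.5% to 29.9%. This assumes all 15 places are filled, independence as stated, and rates that the protocol itself presumes are too high for this procedure. No aim or analysis is affected.

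Two stronger conclusions are tempting, and neither is supported:

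- **That a particular share of bleeds would go unrecorded.** The documents do not say how many bleeds begin after discharge or how many patients would fail to mention one. Any percentage would simply reflect the share assumed.
- **That a formal pause rule is needed.** Take a pause after any perforation or a second bleed. At the cited rates it would be triggered with probability 4.2% to 8.5%. Even if the pause were permanent and 2% of patients bled, an average of 0.161 procedures would remain after the second bleed, so 0.161 × 0.02 = 0.003 bleeds would be averted.

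**What to change.** Add the following to the Visit 4 section and to Risks of Endoscopic Mucosal Resection:

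> Study staff will telephone each EMR patient on a fixed day after the procedure, the day to be chosen by the investigators, to ask about rectal bleeding and symptoms of perforation, and will record the answers. On the two-day schedule the same questions will also be asked at the SmartPill visit the next day and at Visit 3 or the results contact.

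The next-day questions fit within the adverse-event assessment already required at the ingestion visit.

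The cost is one short paragraph in an amendment and at most 15 brief calls by existing staff. Over the planned two-year enrolment that is one call about every 104/15 = 6.9 weeks, if procedures are evenly spread (an assumption). No extra patients, visits, procedures or committee are needed.

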### **Risks of Sedation**

Sedation helps with comfort but carries a risk of reactions, such as low blood pressure or slowed heart rate or breathing. Vitals will be monitored throughout the procedure. Bruising at the IV site is a possibility.

### **Unknown Risks**

There may be other risks of SmartPill Tests or EMR that are currently unknown.

### **Other Risks**

Filling out the questionnaires could cause the subject distress. It is voluntary and if the patient is upset, the questionnaires can be terminated.

## **POTENTIAL BENEFITS**

There is no direct benefit to healthy subjects for participation in this study. Results from the study will help to further understand the disease and possibly lead to better diagnosis and treatment of gastrointestinal symptoms in patients with Fabry disease in the future.

## **MONITORING AND QAULTY ASSURANCE**

The PI and protocol investigators will monitor the study in accordance with the IRB-approved protocol. The investigators will be responsible for completing source documents. An investigator or study coordinator fully trained in human clinical trials will be responsible for verifying source documents, maintaining the electronic enrollment log and database and making sure informed consent is up to date. Adverse events will be reported immediately. Outcomes will be analyzed in an ongoing manner.

Data will be maintained electronically on REDCap, a Partners approved data repository, by the research coordinator copying the subject forms.

Coded information from this study will be shared with the sponsor, Genzyme Corporation. The data that is shared will be coded results with no identifiable information. The principle investigator will retain the key to the code at Partners.

